4.3.1 Screening/Baseline Period (Visit 1, 2/Week -2, -1)

Subjects that meet all criteria of the study will be given an informed consent form to review and sign. Subjects will be required to complete all screening assessments within the 2 weeks prior to randomization and start of treatments.

Screening assessments and pre-treatment:

- 1) Demographic information: gender, age, race, socio-economic status.
- 2) Medical history: medical problems, surgeries, trauma, history of previous ulcers, amputations, characteristic and duration.
- 3) Physical examination: vital signs, height, weight, Body Mass index
- 4) General health and lifestyle: smoking history, alcohol, drugs abuse, regular physical activity.
- 5) Lower extremity exam: vascular - pedal pulses, color of skin, temperature, edema; dermatological – clinical description of the ulcer (staging per UT wound classification), fungal infection of skin and/or nails, skin integrity (calluses, dryness); musculoskeletal – foot deformities such as bunion, hammertoe, bony prominence, fat pad atrophy, altered gait; neurological – absence or presence of sensation with 5.07/10 Semmes-Weinstein monofilament, reflexes.
- 6) Non-invasive vascular study: ankle-brachial systolic pressure (ABI) and toe-brachial systolic pressure (TBI). In order to meet criteria, ankle-arm index must be equal to or greater than 0.8 and less than 1.4 or a toe-arm index is equal to or greater than 0.6.
- 7) Foot ulcer history (location, length of time, treatments used, pain, etiology of ulcer).
- 8) Laboratory: HgA1c, chemistry, CBC, pregnancy test (for women of childbearing ages), LFT, ESR, CRP and albumin.

- 9) Radiological imaging – plain foot and/or ankle films for baseline.
- 10) Subjects will be given the health-related quality of life survey, the Medical Outcomes Study 36 item Short Form (SF-36v2™) health survey.
- 11) Sharp debridement of ulcer will be performed per standard method. A small sample will be collected for microbiology (gram stain, cultures/sensitivities, and fungal) and pathology.
- 12) Photographs of ulcer will be obtained before and after debridement, using Silhouette Mobile™ ulcer tracing, surface area calculation.
- 13) Dressings applied will include non-adhesive dressing (Adaptic® or Mepitel®), Iodosorb® gel over wound bed, covered by dry dressings.
- 14) Off-loading shoes will be given, modified offloading insert (trilaminar plastazote) as determined appropriate per discretion of clinician.

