- Number of incident subjects with infection, osteomyelitis and acute Charcot during the study, will be withdrawn from the study.
- Number of incidence of adverse effects will be reported from all sites, and will be withdrawn from the study.
- Veterans' Short Form Health Survey (SF-36v2TM), a self-administered questionnaire will be used to measure quality of life, given at beginning and at the end of the study.
- EuroQol Questionnaire (EQ-5D) to evaluate overall quality of life and to facilitate the calculation of health utilities and quality adjusted life years (QALYs). The EuroQol questionnaire (EQ-5D) will be administered at beginning and at the end of the study.

Sample Size Estimation:

The sample size was estimated based on 80 percent power, significance level 0.05, to detect a difference in the incidence of ulcer closure of the two study groups and the standard of care group (Stplan4.3).⁴ It is expected that 50% of the Dermagraft® and Oasis® groups will reach complete ulcer closure by Week 12 and approximately 25% closure with those subjects that received the standard of care (numbers based on previous studies as described previously). We would expect the difference to be 25% between the standard and the treatment group. By using a Chi-square test without continuity correction test would require 57 subjects in each group. If we estimate the difference to be 20% and lower of the cure rates to be 30%, then we would require 88 patients in each group.

Analyses:

The primary end point is wound closure by Week 12, which will be analyzed using Chi-square test to compare the percentages of subjects with complete closure in each group. We will also perform exploratory analysis with logistic regression, using the complete closure at 12 weeks as the dependent variable and the independent variables would include, treatment, size of ulcer, location on foot, how long ulcer has been present, previous revascularization (will analyze as subset group), offloading compliance, concomitant medications, foot deformity, history of amputation, diabetes complications index, and glucose control (HbA1c). Selection of covariates will be performed by stepwise modeling procedures.

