We will perform a cost-effectiveness analysis comparing the treatment groups Dermagraft®, Oasis® and the standard care group at the NCHCS using ANOVA or Kruskal-Wallis test depending if data is normally distributed for comparison of the three treatment arms. If significant, we will further analyze with pair-wise comparisons by using t-test or Wilcoxon rank-sum test with the Bonferroni correction to control for type I experiment-wise error rate of 0.05. A p-value less than $0.05/3 = 0.0167$ will be considered statistically significant.

We will evaluate the cost-effectiveness of the Oasis® compared to Dermagraft® and the standard of care by measuring QALYs as the measure of effectiveness, based on results obtained from SF-36v2™ questionnaire. Multiple regression will be used to allow to evaluate continuous dependent variable outcomes, including change scores between baseline and end of study physical (PCS) and mental (MCS) component summaries from the SF-36v2™ questionnaire.

Rates of healing among the three groups will be analyzed using log-rank test to compare time of healing within 20 weeks among the 3 treatment groups.

Secondary endpoint (complete healing at 20 weeks), recurrence ulceration rate at 20 weeks will be analyzed using Chi-square tests. In addition, demographics, smoking history, and characteristics of the wound will also be summarized in table. Data that are continuous variables will be summarized by using mean, median, standard deviation, coefficient of variation, minimum and maximal values. Frequency tables will summarize categorical variables.

Timeline and Milestones:

Months	Year 1		Year 2	
	1-6	7-12	1-6	7-12
Aim 1: Recruitment				
Step 1: Screening (2-week run-in phase)	✓	✓	✓	
Step 2: Randomization/Assignment	✓	✓	✓	
Aim 2: Data Collection				
Step 1: Healed by Week 12	✓	✓	✓	✓
Step 2: Wound not healed by Week 12, continue in study until Week 20	✓	✓	✓	✓
Step 3: If wound has not reached closure beyond the 8 weeks of Dermagraft® – will switch to standard of care (expensive). Oasis® – continue to the end of study	✓	✓	✓	✓
Aim 3: Data Analysis				
Step 1: Outcome effectiveness If outcome show significant difference will cross over for intent-to-treat	✓	✓	✓	✓

7 References

1. Vista/CPRS data record system from 2006-2008, retrieved on 4/7/2009.
2. Vista/CPRS data record system from 2006-2008, retrieved on 4/7/2009.

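### The PCS and MCS regression models change scores but lists no covariates, so nothing commits it to adjusting for the baseline score

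*Combined protocol and SAP*

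**What the plan says.** The quality-of-life analysis is described in the Protocol Summary (Quality of Life Assessment), in Section 6 (Analyses) and in the Statistical Analysis Plan, in nearly identical words. The method is "Multiple regression will be used to allow to evaluate continuous dependent variable outcomes", and the outcomes of interest are named as "including change scores between baseline and end of study physical (PCS) and mental (MCS) component summaries". The description ends there: no regressors are listed in any of the three places.

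The analysis text has one covariate list, and it belongs to a different model, the exploratory logistic model of closure: "using the complete closure at 12 weeks as the dependent variable and the independent variables would include, treatment, size of ulcer, location on foot", followed by further clinical factors. It contains no SF-36 score. The statement that "Selection of covariates will be performed by stepwise modeling procedures" also follows that logistic model.

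The baseline score will be available. Section 4.3.1 says at screening: "Subjects will be given the health-related quality of life survey, the Medical Outcomes Study 36 item Short Form (SF-36v2™) health survey". Section 6 describes the SF-36v2 as "a self-administered questionnaire will be used to measure quality of life, given at beginning and at the end of the study".

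**The concern.** Subtracting the baseline is the only handling of it that the plan commits to. A change score fixes the coefficient of baseline at 1. With similar SDs at both visits, the regression slope of follow-up on baseline is r, which is below 1, so subtraction over-corrects. An arm that happens to start lower will then tend to show a larger gain with no treatment effect.

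Section 3 names age, gender, race, date of diabetes diagnosis and ulcer size as balancing factors. Baseline quality of life is not among them, so PCS and MCS are balanced only by chance.

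Two things are at stake. One is precision, in a comparison for which the trial was not sized. The other is an open choice between two analyses with different estimates and standard errors, which could be settled after the data are seen.

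**Working it through.** **Inputs from the documents.** There are three arms of 57 (171 in total), with about 20% dropout assumed in Section 3. The number 57 comes from closure rates, not quality of life: "The sample size was estimated based on 80 percent power, significance level 0.05" and "It is expected that 50% of the Dermagraft® and Oasis® groups will reach complete ulcer closure by Week 12", against about 25% with standard care. The plan gives no SD, correlation, target difference or power for PCS or MCS.

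**The plan's own figure.** The two-proportion formula for 25% v 50% (two-sided 0.05, 80% power, no continuity correction) gives 57.67, or 58 rounded up. At 57 per arm the power is 79.5%. The stated 57 therefore reproduces to within rounding. Here it is simply the number available for the PCS and MCS comparison.

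**Variance.** Let the score have SD s at both times (assumed) and baseline to follow-up correlation r (assumed).

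- Change score without baseline: 2(1 − r)s².
- With baseline as covariate: (1 − r²)s².
- Ratio: (1 − r²) / [2(1 − r)] = (1 + r)/2, so the reduction is (1 − r)/2.

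The direction does not depend on equal SDs. With SDs s_B and s_Y, the first variance minus the second is s_B² + s_Y² − 2r·s_B·s_Y − (1 − r²)s_Y² = (s_B − r·s_Y)², which is never negative.

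**Consequences at 57 per arm.** For one pairwise contrast in SD units, SE = √(2v/57), where v is the variance above with s = 1. The difference detectable with 80% power at two-sided 0.05 is (1.960 + 0.842) × SE. Each cell reads without → with baseline.

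| r (assumed) | Variance ratio | SE | Detectable difference (SD) | Power for 0.5 SD |
|---|---|---|---|---|
| 0.3 | 0.65 | 0.222 → 0.179 | 0.621 → 0.501 | 62% → 80% |
| 0.5 | 0.75 | 0.187 → 0.162 | 0.525 → 0.454 | 76% → 87% |
| 0.7 | 0.85 | 0.145 → 0.134 | 0.406 → 0.375 | 93% → 96% |
| 0.9 | 0.95 | 0.084 → 0.082 | 0.235 → 0.229 | about 100% both |

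The 0.5 SD difference is a yardstick, not a value from the plan. With 20% dropout, 57 × 0.8 = 45.6. At 45 per arm and r = 0.5, power goes from 66% to 78%.

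**Shift from a chance imbalance.** If two arms differ at baseline by d, the unadjusted change-score contrast moves by −(1 − r)d. A one-standard-error imbalance is d = √(2/57) = 0.187 SD. The size of the shift is then 0.13, 0.09, 0.06 and 0.02 SD at r = 0.3, 0.5, 0.7 and 0.9.

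**Bias on average.** Over 5,000 simulated trials (171 subjects, r = 0.5, no true effect), the mean estimate was 0.002 for both methods. The empirical SEs were 0.187 (change only) and 0.163 (with baseline). The squared ratio, 0.163²/0.187² = 0.76, agrees with the formula's 0.75.

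**Change score or end score.** In one simulated data set, regressing change on treatment and baseline gave treatment effects of −0.129 and 0.021, each with SE 0.154. Regressing the end score on the same terms gave the same effects and SEs; only the baseline coefficient differed, by exactly 1 (−0.440 v 0.560). Without baseline, the effects were −0.106 and 0.066, each with SE 0.170.

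**The case against.** The strongest reply is that the plan never says baseline is left out. A reader might infer that PCS and MCS will be analysed as raw changes with no baseline term, but the documents do not support that. They name a multiple regression, which implies regressors beyond treatment, and do not list them. The logistic covariate list serves another outcome, so the absence of an SF-36 score there shows nothing about this model. If baseline is one of the unlisted regressors, there is no defect: the treatment estimate is the ANCOVA estimate. The change score as dependent variable is therefore not an error in itself.

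A reader might also infer that the planned comparison is biased. Under randomisation it is not, on average; only the estimate conditional on an observed imbalance shifts. Nor is a 15–35% gain a property of this plan: it holds for r between 0.3 and 0.7, and at r = 0.9 the gain is 5%.

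Finally, PCS and MCS are not among the listed efficacy outcomes, and no decision rule rests on them.

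All of this stands, and it limits the point. It does not remove it: the text permits both models, they give different answers, and the better one costs nothing. The scores are also not idle, since the plan bases its QALY measure of effectiveness on SF-36v2 results.

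**Conclusion.** The point holds as a gap in specification with a free improvement attached. The covariates of the PCS and MCS regression are not stated, and nothing commits the model to the baseline score. If it is fitted without baseline, the variance of the contrast is higher than it need be, and adding baseline would cut it by 35%, 25%, 15% or 5% at r = 0.3, 0.5, 0.7 or 0.9. A one-standard-error imbalance would shift the unadjusted contrast by between 0.13 and 0.02 SD over the same range.

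These sizes rest on equal SDs at the two visits, on assumed correlations, on 57 analysed per arm, and on baseline in fact being omitted. Severity is low because the outcome is supportive.

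**What to change.** Add one sentence to Section 6 and the Statistical Analysis Plan, and match it in the Protocol Summary: PCS and MCS will each be regressed on treatment and the corresponding baseline score, with baseline forced into the model and not subject to stepwise selection, and adjusted mean differences between arms will be reported with 95% CIs. Either the end-of-study score or the change score may be the dependent variable, since the treatment estimate is the same. Site and the balancing factors are a separate question that this point does not settle.

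The cost is the sentence itself; the baseline SF-36v2 is already scheduled at Visit 1. The same edit should name the end-of-study assessment, because the Section 4.3 flow chart places the second questionnaire at Visit 20 and Section 4.3.4 places it at Visit 19 (Week 16). Those two places need reconciling before the outcome has a single time point.

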2 OBJECTIVES

The primary objective of this study is to assess the effectiveness of cellular dermal replacement tissue vs. non-viable extracellular matrix (ECM) for the treatment of non-healing diabetic foot ulcers. The primary endpoint will be the measurement of wound closure at 12 weeks, secondary outcomes will be measured at 20 weeks and the rate of healing in each treatment arm.

The secondary objective of study is to determine cost effectiveness of the bioengineered cellular vs. acellular ECM products. Cellular ECMs (Dermagraft®) are costly devices, \$1800 per application, difficult to use and time sensitive (weeks). The acellular ECM (Oasis®) is easier to use and at a cost \$80 per application and has a longer shelf life (2 years). These devices typically require multiple applications, on a weekly basis. If the findings show that these devices are equivalent, then the use of acellular ECM would lead to significant savings for the VA. Genetic markers of non-healing vs. healing diabetic ulcers will also be investigated, which will be useful information in predicting healing potential.

[figure not shown]

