Tenderness/Pain at Wound Site (pain scale 0-10):

- A. None
- B. 1 to 2
- C. Greater than 3 to 4
- D. Greater than 4 to 7
- E. 8 to 10

Statistical Analysis Plan

Analyses: The primary outcome is wound closure by Week 12, which will be analyzed using Chi-square test to compare the percentages of subjects with complete closure in each group. We will also perform exploratory analysis with logistic regression, using the complete closure at 12 weeks as the dependent variable and the independent variables would include, treatment, size of ulcer, location on foot, how long ulcer has been present, previous revascularization (will analyze as subset group), offloading compliance, concomitant medications, foot deformity, history of amputation, diabetes complications index, CRP level, and glucose control (HbA1c). Selection of covariates will be performed by stepwise modeling procedures, and overseen by biostatistician [name].

Cost effectiveness analysis: We will perform a cost-effectiveness analysis comparing the treatment groups Dermagraft®, Apligraf®, Oasis® and the standard care group at the NCHCS using ANOVA or Kruskal-Wallis test depending if data is normally distributed for comparison of the three treatment arms. If significant, we will further analyze with pair-wise comparisons by using t-test or Wilcoxon rank-sum test with the Bonferroni correction to control for type I experiment-wise error rate of 0.05. A p-value less than $0.05/3 = 0.0167$ will be considered statistically significant.

We will evaluate the cost-effectiveness of the Oasis® compared to Dermagraft® or Apligraf® and the standard of care by measuring QALYs as the measure of effectiveness, based on results obtained from SF-36v2™ questionnaire. Multiple regression will be used to allow to evaluate continuous dependent variable outcomes, including change scores between baseline and end of study physical (PCS) and mental (MCS) component summaries from the SF36v2™ questionnaire.

Rates of healing among the four groups will be analyzed using log-rank test to compare time of healing within 20 weeks.

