Secondary outcomes such as complete healing at 20 weeks, recurrence ulceration rate at 20 weeks will be analyzed using Chi-square tests. In addition, demographics, smoking history, and characteristics of the wound will also be summarized in table. For comparison nominal categorical secondary outcome variables, we will use Chi-square test. For comparison of ordinal categorical variables, we will use the Wilcoxon rank-sum test (for two independent group comparison) and Kruskal-Wallis test (for three independent group comparison).

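### Time to healing and Week 20 closure have no named Oasis–Dermagraft contrast or effect estimate, and the overall log-rank test is about equally likely to be significant whichever arm Oasis resembles

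*Combined protocol and SAP*

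**What the plan says.** Section 2 (Objectives) states the primary aim as to "assess the effectiveness of cellular dermal replacement tissue vs. non-viable extracellular matrix (ECM) for the treatment of non-healing diabetic foot ulcers". The Protocol Summary lists Week 20 closure and rate of healing among the secondary efficacy outcomes.

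- **Time to healing.** Section 6 (Analyses): "Rates of healing among the three groups will be analyzed using log-rank test to compare time of healing within 20 weeks". The Statistical Analysis Plan at the end of the document has "Rates of healing among the four groups will be analyzed using log-rank test to compare time of healing within 20 weeks", and the Protocol Summary (Data Analysis) also speaks of four groups.
- **Week 20 closure.** The Statistical Analysis Plan: "Secondary outcomes such as complete healing at 20 weeks, recurrence ulceration rate at 20 weeks will be analyzed using Chi-square tests". Section 6 says the same in substance. Neither gives the number of groups or a contrast.
- **Pairwise step.** One is written, but only after the ANOVA or Kruskal-Wallis test on cost-effectiveness: "If significant, we will further analyze with pair-wise comparisons by using t-test or Wilcoxon rank-sum test with the Bonferroni correction", at 0.05/3 = 0.0167.
- **Two-group tests.** The Protocol Summary and Statistical Analysis Plan name a two-group Wilcoxon test, but for ordinal variables.

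No passage asks for a hazard ratio, risk difference or confidence interval for these two outcomes.

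**The concern.** A test across three arms has 2 degrees of freedom and asks only whether any arm differs from another. Under the plan's own expectation, with both products at 50% and standard care at 25%, it will usually reject because standard care is lower. That says nothing about Oasis against Dermagraft, the comparison on which adoption of the cheaper matrix depends. A significant result would be about as likely if Oasis did no better than standard care.

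The pairwise step for cost cannot be borrowed. A t-test or Wilcoxon test suits neither censored healing times nor a yes/no outcome. The logistic regression does not fill the gap either: it is exploratory and models Week 12 closure.

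**Working it through.** **Inputs from Section 6 (Sample Size Estimation).** "The sample size was estimated based on 80 percent power, significance level 0.05"; "It is expected that 50% of the Dermagraft® and Oasis® groups will reach complete ulcer closure by Week 12 and approximately 25% closure" on standard care; "By using a Chi-square test without continuity correction test would require 57 subjects in each group". Section 3 assumes about 20% dropout.

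**1. The plan's own figure.** Two-sided, pooled variance, no continuity correction:

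n = [1.96·√(2·0.375·0.625) + 0.842·√(0.25·0.75 + 0.50·0.50)]² / 0.25² = 57.7.

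The stated 57 is reproduced within rounding (the arcsine form gives 57.3); power at 57 is 79.5%. It contains no dropout allowance, so a 20% loss leaves 57 × 0.8 ≈ 46 per arm.

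**2. Healing times (assumption).** The documents give no healing-time distribution and no Week 20 rates. A constant hazard through the Week 12 rates is λ = −ln(1 − p)/12, or 0.0578 per week at 50% and 0.0240 at 25%. The hazard ratio is ln 0.50 / ln 0.75 = 2.41. Week 20 closure is 1 − 0.50^(20/12) = 68.5% and 1 − 0.75^(20/12) = 38.1%.

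**3. Overall tests in two opposite cases.** Case A: Oasis equals Dermagraft, standard care lower. Case B: Oasis equals standard care, Dermagraft higher. The chi-square noncentrality shows why they look alike: n·Σ(pᵢ − p̄)² / [p̄(1 − p̄)]. With 25% and 50%, Σ(pᵢ − p̄)² = 0.0417 in both cases and only p̄ changes.

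- A: 57 × 0.0417 / (0.417 × 0.583) = 9.77
- B: 57 × 0.0417 / (0.333 × 0.667) = 10.69

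The large-sample approximation turns these into 80.6% and 84.2%; simulation gives 83.1% and 84.0%. Simulated probabilities of a significant overall test at 0.05 (log-rank: 20,000 trials, weekly assessment, censoring at Week 20; chi-square: 400,000 trials):

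| Test | Per arm | Lower/higher rate | Case A | Case B |
|---|---|---|---|---|
| Log-rank | 57 | 25%/50% at Week 12 | 94.7% | 95.3% |
| Log-rank | 57 | 30%/50% at Week 12 | 77.9% | 79.9% |
| Log-rank | 46 | 25%/50% at Week 12 | 88.6% | 90.5% |
| Week 20 chi-square | 57 | 38%/69%, extrapolated | 94.0% | 93.9% |
| Week 20 chi-square | 57 | 25%/50%, carried forward | 83.1% | 84.0% |
| Week 20 chi-square | 57 | 35%/60%, assumed | 80.5% | 80.9% |
| Week 20 chi-square | 57 | 30%/50%, carried forward | 61.2% | 62.4% |
| Week 20 chi-square | 46 | 25%/50%, carried forward | 73.1% | 74.9% |

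The 30%/50% pair is the plan's own alternative sample-size scenario.

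**4. The named contrast, 57 per arm.** Power ≈ Φ(√(D/4)·ln HR − z), where D is closures in the two arms.

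- Case B: D = 57 × (0.685 + 0.381) = 60.8. √(60.8/4) × ln 2.41 = 3.43, so power is 92.9% at 0.05 and 84.9% at 0.0167.
- Case A: the pairwise log-rank rejects in 5.2% of simulated trials, its nominal level.
- Oasis 35% against Dermagraft 50% at Week 12: HR = ln 0.50 / ln 0.65 = 1.61; D = 57 × (0.685 + 0.512) = 68.2; √(68.2/4) × ln 1.61 = 1.96, so power is about 50%.
- Week 20 pairwise chi-square in case B: 91.3% at 0.05 and 81.7% at 0.0167 with extrapolated rates; 79.5% and 64.6% with 25%/50% carried forward.

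**5. Precision if Oasis equals Dermagraft.**

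- Hazard ratio, 57 per arm: 57 × 0.685 = 39 closures each; SE(log HR) = √(2/39) = 0.226; the 95% interval is ×/÷ exp(1.96 × 0.226) = 1.56.
- Hazard ratio, 46 per arm: 31.5 closures each; SE = √(2/31.5) = 0.252; ×/÷ 1.64.
- Week 20 risk difference, 57 per arm: half-width 1.96·√(2·0.685·0.315/57) = 17 points, or 18 points if closure is 50%.

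**The case against.** **Any overall test behaves this way.** With equal arms it is nearly symmetric in which arm is the odd one out, so the near-equality is a property of the design rather than a discovery. That is true. It is also why the overall p-value cannot carry the Oasis–Dermagraft question.

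**Readers see more than a p-value.** One might infer that the results could not show which arm differs. The documents do not support that. Section 6 makes the percentage closed by Week 12 and Week 20 a clinical outcome and provides frequency tables. In case B a pattern near 38%, 69% and 38% would be visible. What is missing is a prespecified contrast, an interval and error control.

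**A single Week 20 test is an inference.** The overall test across groups is explicit only for the log-rank. For Week 20 it is the natural reading; the certain fact is that no contrast is named.

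**The 94–95% level is optimistic.** It rests on constant hazard and no dropout. Section 4.3.3 returns unhealed ulcers to standard care after the eighth application, and Section 6 withdraws subjects with infection or adverse events. The levels do move, as the table shows; the closeness of the two cases does not.

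**A pairwise difference test does not show equivalence.** This stands. The plan states no margin, and the test misses a 35% versus 50% difference about half the time. The estimate and its interval should therefore lead.

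**Conclusion.** The point holds for the two clinical secondary outcomes. As written, neither analysis yields a prespecified Oasis–Dermagraft comparison or estimate. At 57 per arm the overall log-rank is significant in about 94–95% of trials in either of two opposite situations, and at 46 per arm in about 88–91%. These levels assume constant hazard through the stated Week 12 rates, with no dropout beyond the reduction to 46. Under the other rates tried the level falls, to about 61–62% at the lowest in the table, but the two cases remain within about 2–3 points.

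This is a gap in specification. It does not make the log-rank or chi-square test wrong, and it does not make the trial's results unreadable. Naming the contrast locates a difference; it does not by itself establish equivalence.

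**What to change.** In the Protocol Summary (Data Analysis), Section 6 (Analyses) and the Statistical Analysis Plan:

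1. Name Oasis versus Dermagraft as the lead contrast for time to healing and Week 20 closure, with each product versus standard care as the other two.
2. Report the Oasis/Dermagraft hazard ratio and Week 20 risk difference with 95% confidence intervals whatever the overall test shows, as the main basis for interpretation.
3. Reconcile the number of arms. Sections 4.1 and 4.3.2 describe three; the Protocol Summary and Statistical Analysis Plan speak of four groups for the log-rank, and the latter lists Apligraf in the cost analysis.
4. Follow a significant overall test with pairwise log-rank tests and pairwise Week 20 chi-square tests. With exactly three arms, 0.05 for each holds the error for that outcome at 0.05, because any two pairwise nulls together imply that all three arms are equal. With four arms this fails. If the arm count is not settled, use the plan's own 0.0167 for the three named contrasts.
5. State that a non-significant pairwise test is not evidence of equivalence.

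The cost is wording and a few lines of output, with no new data or patients. The downside is a visibly wide interval (hazard ratio ×/÷ about 1.56 at 57 per arm, 1.64 at 46) and a pairwise log-rank with only about 50% power for 35% versus 50%.
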